## 6 DOSING DELAYS/DOSE MODIFICATIONS

### 6.1 Trametinib and/or GSK2141795 Dose Modifications

The table below outlines the dose levels to be used for any necessary trametinib dose modifications when dosing trametinib as a single agent:

Dose Level	Trametinib Dose/Schedule
0	2 mg QD
-1	1.5 mg QD
-2	1 mg QD

If GSK2141795 is added for disease progression after 2 cycles or because of failure to achieve a PR after 4 cycles then the dose of trametinib will be reduced to 1.5 mg and combined with 50 mg pf GSK2141795 administered daily.

The table below outlines the dose levels to be used for any necessary trametinib dose modifications when trametinib is dosed with GSK2141795:

Dose Level	Trametinib Dose/Schedule
0	1.5 mg QD
-1	1.0 mg QD
-2	0.5 mg QD

The table below outlines the dose levels to be used for any necessary GSK2141795 dose modifications:

Dose Level	GSK2141795 Dose/Schedule
0	50 mg QD
-1	25 mg QD

A maximum of two Trametinib and/or one GSK2141795 dose level reductions are allowed. Patients may have up to 2 dose level reductions of Trametinib while taking Trametinib alone (lowest dose allowed is 1 mg QD). Patients may have a further 2 dose level reductions of Trametinib while taking Trametinib in combination with GSK2141795 (lowest dose allowed is 0.5 mg QD).

6.1.1 Trametinib or GSK2141795 Dose Modification for Toxicities Hematological/ Non-Hematological Toxicities Not Otherwise Specified in Subsequent Sections

The investigator should use clinical judgment to determine which drug may be contributing to the toxicity necessitating dose adjustment and make the appropriate change for that drug.

Study Drug(s) Modification for Clinically Significant Toxicities Deemed Related to Study Drug(s) (This section is not for specific AEs such as hypertension, rash, ejection fraction changes, pneumonitis, diarrhea, liver chemistry, QTc prolongation, visual changes, neutropenia, or thrombocytopenia. Refer to other sections for these specific AEs).		
CTCAE v4 Grade	Management Guideline	Dose Modification
Grade 1	Monitor as clinically indicated. Provide supportive care according to institutional standards	Continue trametinib and/or GSK2141795 at current dose level.
Grade 2		
 
• Interrupt trametinib and/or GSK2141795 until resolution to grade 1 or baseline.
 
• Upon resolution, restart trametinib and/or GSK2141795 at current dose level.
 

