Grade 3		
 
• Interrupt trametinib and/or GSK2141795 until resolution to grade 1 or baseline.
 
• Upon resolution to baseline or grade 1, restart the interrupted agent(s) with one level of dose reduction
 
• If the Grade 3 toxicity recurs, interrupt trametinib and/or GSK2141795; When toxicity resolves to Grade 1 or baseline, restart the interrupted agent(s) reduced by another dose level
 

Grade 4		Permanently discontinue trametinib and/or GSK2141795.
Study drug(s) should be discontinued if treatment delay is $\geq 28$ days due to toxicities. If the investigator concludes that continued study drug(s) will benefit a patient, the study chair and CTEP Medical Monitor may be consulted for the possibility of resuming study drug(s), provided that toxicities have resolved to baseline or grade 1.		

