### 6.1.7 Trametinib Dose Modification for Reduced Left Ventricular Ejection Fraction

Decreases of the left ventricular ejection fraction (LVEF) have been observed in patients receiving trametinib. Therefore, ECHOs must be performed in regular intervals outlined in the Study Calendar. The same procedure (either ECHO or MUGA, although ECHO is preferred) should be performed at baseline and at follow-up visit(s).

Trametinib Dose Modification Guidelines and Stopping Criteria for LVEF Decrease		
Clinic	LVEF-drop (%) or CTCAE grade	Action and Dose Modification
Asymptomatic	Absolute decrease of >10% in LVEF compared to baseline and ejection fraction below the institution's LLN.	
 
• Interrupt trametinib and repeat ECHO/MUGA within 2 weeks.a
 
• If the LVEF recovers within 4 weeks (defined as LVEF ≥ LLN and absolute decrease ≤ 10% compared to baseline):               
 
– Consult with the CTEP trametinib medical monitor and request approval for restart.
 
– Restart treatment with trametinib at reduced dose by one dose level.b
 
– Repeat ECHO/MUGA 2, 4, 8, and 12 weeks after re-start; continue in intervals of 12 weeks thereafter.
 
 
 
• If LVEF does not recover within 4 weeks:               
 
– Consult with cardiologist.
 
– Permanently discontinue trametinib.
 
– Report as SAE
 
– Repeat ECHO/MUGA after 2, 4, 8, 12, and 16 weeks or until resolution.
 
– Consult with the CTEP trametinib medical monitor.c
 
 
 

Symptomaticb	
 
• Grade 3: resting LVEF 39-20% or >20% absolute reduction from baseline
 
• Grade 4: Resting LVEF ≤ 20%.
 
	
 
• Permanently discontinue trametinib.
 
• Report as SAE.
 
• Consult with cardiologist.
 
• Repeat ECHO/MUGA after 2, 4, 8, 12, and 16 weeks or until resolution.
 

a If ECHO/MUGA does not show LVEF recovery after 2 weeks, repeat ECHO/MUGA 2 weeks later.  
b Escalation of trametinib to previous dose level can be considered if LVEF remains stable for 4 weeks after restarting of trametinib. Approval from the CTEP trametinib medical monitor is required.  

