**Version 2.3, October 26, 2015**

Adverse Events with Possible Relationship to Trametinib dimethyl sulfoxide (GSK1120212B) (CTCAE 4.0 Term) [n= 968]			Specific Protocol Exceptions to Expedited Reporting (SPEER)
Likely (>20%)	Less Likely (<=20%)	Rare but Serious (<3%)	
BLOOD AND LYMPHATIC SYSTEM DISORDERS			
	Anemia		Anemia (Gr 2)
CARDIAC DISORDERS			
		Heart failure	
		Left ventricular systolic dysfunction	
	Sinus bradycardia		
EYE DISORDERS			
	Blurred vision		
	Dry eye		
		Eye disorders - Other (chorioretinopathy also known as retinal pigment epithelial detachment)	
		Eye disorders - Other (retinal vein occlusion)	
	Eye disorders - Other (visual disorders) 		
GASTROINTESTINAL DISORDERS			
	Abdominal pain		Abdominal pain (Gr 2)
	Constipation		Constipation (Gr 2)
Diarrhea			Diarrhea (Gr 3)
	Dry mouth		Dry mouth (Gr 2)
	Dyspepsia		Dyspepsia (Gr 2)
	Mucositis oral		Mucositis oral (Gr 2)
Nausea			Nausea (Gr 3)
	Vomiting		Vomiting (Gr 3)
GENERAL DISORDERS AND ADMINISTRATION SITE CONDITIONS			
	Chills		Chills (Gr 2)

Adverse Events with Possible Relationship to Trametinib dimethyl sulfoxide (GSK1120212B) (CTCAE 4.0 Term) [n= 968]			Specific Protocol Exceptions to Expedited Reporting (SPEER)
Likely (>20%)	Less Likely (<=20%)	Rare but Serious (<3%)	
	Edema face		
Fatigue			Fatigue (Gr 3)
	Fever		Fever (Gr 2)
IMMUNE SYSTEM DISORDERS			
	Allergic reaction 		
INFECTIONS AND INFESTATIONS			
	Paronychia		Paronychia (Gr 2)
	Skin infection		Skin infection (Gr 2)
INVESTIGATIONS			
	Alanine aminotransferase increased		Alanine aminotransferase increased (Gr 2)
	Alkaline phosphatase increased		Alkaline phosphatase increased (Gr 2)
	Aspartate aminotransferase increased		Aspartate aminotransferase increased (Gr 2)
	CPK increased		
	Ejection fraction decreased		
METABOLISM AND NUTRITION DISORDERS			
	Anorexia		Anorexia (Gr 2)
	Dehydration		Dehydration (Gr 3)
	Hypoalbuminemia		
	Hypomagnesemia		Hypomagnesemia (Gr 2)
	Hyponatremia		Hyponatremia (Gr 3)
MUSCULOSKELETAL AND CONNECTIVE TISSUE DISORDERS			
	Arthralgia		
	Back pain		Back pain (Gr 2)
		Musculoskeletal and connective tissue disorder - Other (rhabdomyolysis)	
	Pain in extremity		Pain in extremity (Gr 2)
NERVOUS SYSTEM DISORDERS			

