## 10 STUDY CALENDAR

Baseline evaluations are to be conducted within 1 week prior to start of protocol therapy, unless specified differently in the study calendar. Scans and x-rays, ECHO/MUGA, and Ophthalmology exam must be done  $\leq 4$  weeks prior to the start of therapy. In the event that the patient's condition is deteriorating, laboratory evaluations should be repeated within 48 hours prior to initiation of the next cycle of therapy. If pre-study assessments were done within 3 days of treatment initiation, they do not need to be repeated for cycle 1 day 1. For subsequent cycles (2+), day 1 assessments can be completed up to 48 hrs prior to day 1. All day 15 assessments can be completed up to 48 hrs prior to day 15. Baseline myeloma disease assessment can be done  $\leq 4$  weeks prior to the start of therapy (see [11.2.1](#)). Response assessment can be done up to  $\leq 7$  days prior to the start of the next cycle to allow for treatment decisions to be made with regards to the addition of GSK2141795 for stable disease or progression prior the initiation of the next cycle.

PROCEDURES	Screen	Cycle 1-2 Single Agent (cycle=28 days)		Cycles 3+ Single Agent	Cycle 1-2 Combination		Cycles 3+ Combination	Off Study	Safety Follow-up
		Day1	Day15	At the start of every Cycle	Day1	Day 15	At the start of every cycle		
Trametinib		A-----A			A*-----A*				4 weeks (+ 3 days) after last treatment
GSK2141795					B-----B				
Informed consent	X								
Demographics	X								
Medical history	X								
Concurrent meds	X	X-----X						X	
Physical exam	X	X		X	X		X	X	
Vital signs	X	X	X	X	X	X	X	X	
Height	X								
Weight	X	X	X	X	X	X	X	X	
Performance status	X	X	X	X	X	X	X	X	
CBC w/diff, plts	X	X	X	X	X	X	X	X	
Fasting serum chemistry a	X	X	X	X	X	X	X	X	
TSH	X				X		X i	X	
Serum viscosity m	X								
ECG b	X	X	X	X		X		X	
Echocardiogram or MUGA	X	Every 12 weeks (use same methodology for baseline and follow up).							
Ophthalmology exam l	X	as clinically indicated k							
Visual acuity exam k	X	X		X	X		X	X	
Adverse event evaluation		X-----X						X	X i
Myeloma disease assessment c (section 11.2.1)	X	Assessments are repeated every 4 weeks. Documentation must be provided for patients removed from study for progressive disease.						X	

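### Section 6.1.7 has no row for a symptomatic LVEF fall of more than 10 and at most 20 points to between 40% and below LLN, and section 6.1.5 puts liver criterion 2 under two monitoring schedules

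*Combined protocol and SAP*

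**What the plan says.** **LVEF, section 6.1.7.** The asymptomatic row applies to an "Absolute decrease of >10% in LVEF compared to baseline" that also takes LVEF below the institution's LLN. The action is "Interrupt trametinib and repeat ECHO/MUGA within 2 weeks". Restart is one dose level lower, and only if LVEF recovers within 4 weeks and the medical monitor approves. Otherwise the drug is stopped permanently, with a cardiology consult and an SAE report.

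The symptomatic row has two entries. The first is "Grade 3: resting LVEF 39-20% or" an absolute reduction of more than 20% from baseline. The second is grade 4, a resting LVEF of 20% or less. Both lead to permanent discontinuation, an SAE report and a cardiology consult.

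**General toxicity table, section 6.1.1.** Its header says that it is not "for specific AEs such as hypertension, rash, ejection fraction changes, pneumonitis, diarrhea, liver chemistry, QTc prolongation" and the other events named there, and refers the reader to the specific sections.

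**Liver, section 6.1.5.** Patients who stop for criteria 1 or 2 are rechecked within 24 hours and then monitored twice weekly. Patients who stop for criteria 2 to 6 are rechecked within 24 to 72 hours and then monitored weekly. The event column names trametinib as the drug to stop, and the action column names study treatment.

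**The concern.** Section 2.2.1.3 lists cardiac and hepatic events among the adverse events of special interest, and these tables are the operative rules for them at several sites. In 6.1.7 the instruction disappears when symptoms are added to an LVEF fall that would otherwise require interruption. A site would expect the opposite, that symptoms call for at least the same action.

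In 6.1.5, criterion 2 is one of the two patterns that footnote 2 of the table describes as possible severe liver injury. Read literally, the table allows its recheck to wait up to 72 hours and then to be weekly.

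At stake is consistent handling of a small number of patients. The efficacy result is not involved.

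**Working it through.** **Step 1. LVEF rows as rules.** Let b be baseline LVEF, x current LVEF and d = b − x, all in whole percentage points, and let L be the institutional LLN. Eligibility (3.1.10 and 3.2.11) requires b ≥ L.

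- Asymptomatic row: d > 10 and x < L → interrupt.
- Symptomatic row, grade 3: 20 ≤ x ≤ 39, or d > 20 → discontinue permanently.
- Symptomatic row, grade 4: x ≤ 20 → discontinue permanently.

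A symptomatic patient who meets the asymptomatic trigger but neither symptomatic entry satisfies 40 ≤ x < L and 10 < d ≤ 20.

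**Step 2. Example.** The documents do not give L, so assume L = 50%. Take b = 60% and x = 45%, so d = 15.

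- Without symptoms: 15 > 10 and 45 < 50, so interrupt.
- With symptoms: 45 is above 39 and 15 is not above 20, so no row applies.

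**Step 3. Range over the assumed LLN.**

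| Baseline b | x with 10 < d ≤ 20 | Uncovered, L = 50% | Uncovered, L = 55% |
|---|---|---|---|
| 60% | 40–49% | 40–49% | 40–49% |
| 65% | 45–54% | 45–49% | 45–54% |

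The baselines that can fall into the gap are 51–69% at L = 50% and 55–74% at L = 55%. The gap exists for any LLN above 40%, and its width depends on the LLN.

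**Step 4. Other tables.** Every patient in the gap has, by definition, a measured ejection fraction change, which the 6.1.1 header excludes. Section 5.3 allows treatment to stop for an unacceptable adverse event or a change in the patient's condition. That leaves the decision to the investigator and supplies no rule.

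**Step 5. Liver criteria.** The stricter schedule covers {1, 2} and the looser one {2, 3, 4, 5, 6}. The intersection is {2}. Two other lines in the same table, on SAE reporting and on additional work-up, group criterion 2 with criterion 1. The stricter monitoring heading also refers to abnormal bilirubin and INR. With {3, 4, 5, 6} as the looser set, the intersection is empty and all six criteria are still covered.

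**Step 6. Ceiling on patients.** Section 2.2.1.3 reports cardiomyopathy, symptomatic or not, in 14 of 211 trametinib patients in the melanoma phase 3 trial. 14/211 = 6.6%, which agrees with the protocol's rounded 7%. The exact 95% interval is 3.7% to 10.9%. If that rate carried over to myeloma (an assumption):

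- 24 patients: 24 × 0.0664 = 1.6 (0.9 to 2.6).
- 74 patients: 74 × 0.0664 = 4.9 (2.7 to 8.1).

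The group in the gap is a subset of these, and the documents do not give its rate.

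**The case against.** The strongest reply is that 6.1.7 is silent on this patient and does not direct continued dosing. Since the same fall without symptoms requires interruption, a sensible clinician would treat the symptomatic patient at least as strictly, and 5.3 permits stopping. This is fair as a forecast of behaviour. It does not supply the missing row, and the table exists so that sites act alike.

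A reader might infer more: that trametinib would be restarted at full dose without a new LVEF, with the next scheduled ECHO up to 12 weeks away. That needs a site to code the event as heart failure or "Left ventricular systolic dysfunction", which the trametinib CAEPR lists apart from decreased ejection fraction, and then to use the 6.1.1 grade 2 row: "Upon resolution, restart trametinib and/or GSK2141795 at current dose level". (The grade 3 row there does reduce the dose: "Upon resolution to baseline or grade 1, restart the interrupted agent(s) with one level of dose reduction".) The documents do not support this as the expected course. The 6.1.1 header disclaims ejection fraction changes, and the calendar entry "Every 12 weeks (use same methodology for baseline and follow up" does not prevent an unscheduled ECHO in a patient with symptoms.

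On the liver table, the objection is that the overlap is evidently a slip. The SAE, monitoring and work-up lines all group criteria 1 and 2 against a single numeral, treatment stops immediately either way, and INR measurement is not required. This stands as to intent and frequency, but the printed schedules still conflict. A reader might also infer that GSK2141795 could be left running on combination therapy. The action column's reference to study treatment, with the section and table titles, largely settles that both drugs stop.

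Finally, a symptomatic fall of 10 points or less, such as 50% to 42%, also has no row. That is true, but the asymptomatic row does not act on it either, so it is a separate clinical question.

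**Conclusion.** The concern holds in two places. Section 6.1.7 has no instruction for a symptomatic LVEF fall of more than 10 and at most 20 points to between 40% and below LLN, although the same fall without symptoms requires interruption and no other table clearly applies. Section 6.1.5 assigns criterion 2 to two incompatible monitoring schedules. Both are operative safety instructions and should be corrected.

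The size is small. The ceiling of about 1.6 of 24 or 4.9 of 74 patients counts all cardiomyopathy and assumes that the melanoma rate applies. The affected subset is smaller and its rate is unknown. The existence of the LVEF gap needs only an LLN above 40%. The liver overlap matters only when INR is measured and the patient is not on an anticoagulant. The difference in the drug named to stop, and the placing of the LVEF footnotes, are editorial. The ORR design, alpha and power are unaffected.

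**What to change.** **Section 6.1.7.** Add a symptomatic row for any symptomatic absolute LVEF fall of more than 10% to below LLN that does not meet the grade 3 or 4 entries, with action at least as strict as the asymptomatic row:

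- Interrupt trametinib, consult cardiology, report as an SAE, and repeat ECHO/MUGA within 2 weeks.
- Restart one dose level lower only after symptoms have resolved, LVEF has recovered and the medical monitor has approved.
- Otherwise discontinue permanently at 4 weeks.

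Keep permanent discontinuation for a symptomatic LVEF of 39% or lower or a fall of more than 20%. The existing symptomatic row allows no rechallenge, so whether to permit it in the new row is a clinical decision. Permanent discontinuation would also close the gap.

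**Section 6.1.5.** Change the looser monitoring heading from criteria 2–6 to criteria 3–6.

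**Editorial only.** Name the study drug(s) in both liver columns. In 6.1.7, attach the symptom definition (footnote c) to the symptomatic label and remove the re-escalation footnote (b) from it.

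**Cost.** A wording amendment to two tables, with no new scheduled test and no change to sample size or analysis. The downside is possibly a few more interruptions and unscheduled ECHOs.

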### 6.1.8 Trametinib and/or GSK2141795 Dose Modification for QTc Prolongation

Study Drug(s) Withholding and Stopping Criteria for QTc Prolongation	
QTc Prolongation a	Action and Dose Modification

 
• QTcB <math>\geq</math>501 msec, or
 
• Uncorrected QT >600 msec, or
 
• QTcB >530 msec for subjects with bundle branch block
 
	
 
• Interrupt study treatment until QTcB prolongation resolves to grade 1 or baseline.
 
• Test serum potassium, calcium, phosphorus, and magnesium. If abnormal, correct per routine clinical practice to within normal limits.
 
• Review concomitant medication usage for a prolonged QTc.
 
• Restart at current dose level.b
 
• If the event does not resolve or recurs after restarting, permanently discontinue study treatment.
 

Abbreviations: msec = milliseconds; QTcB = QT interval on electrocardiogram corrected using Bazett's formula a Based on an average QTc value of triplicate ECGs. For example, if an ECG demonstrates a prolonged QT interval, obtain two or more ECGs over a brief period, and then use the averaged QTc values of the three ECGs to determine if study treatments should be interrupted or discontinued. b If the QTc prolongation resolves to grade 1 or baseline, the subject may resume study treatment if the investigator and the CTEP trametinib medical monitor agree that the subject will benefit from further treatment.	

### 6.1.9 Trametinib Dose Modification for Hypertension

Increases in blood pressure (BP) have been observed in patients receiving trametinib. Recommendations for BP monitoring and management are provided below.

*Monitoring:* All BP assessments should be performed under the following optimal conditions:

- The subject has been seated with back support, ensuring that legs are uncrossed and flat on the floor.
- The subject is relaxed comfortably for at least 5 minutes.
- Restrictive clothing has been removed from the cuff area, and the right cuff has been selected.
- The subject's arm is supported so that the middle of the cuff is at heart level.
- The subject remains quiet during the measurement.
- In subjects with an initial BP reading within the hypertensive range, a second reading should be taken at least 1 minute later, with the two readings averaged to obtain a final BP measurement. The averaged value should be recorded in the eCRF.
- Persistent hypertension is defined as an increase of systolic blood pressure (SBP) >140 mmHg and/or diastolic blood pressure (DBP) >90 mmHg in three consecutive visits with blood pressure assessments from two readings as described above. Visits to monitor increased blood pressure can be scheduled independently from the per-protocol visits outlined in the study calendar. Ideally, subsequent blood pressure assessments should be performed within 1 week.

Management and Trametinib Dose Modification for Hypertension		
Event	Management Guideline	Dose Modification
Definitions used in the table: - Persistent hypertension: Hypertension detected in two separate readings during up to three subsequent visits. - Well-controlled hypertension: Blood pressure of SBP $\leq$ 140 mmHg and DBP $\leq$ 90 mmHg in two separate readings during up to three subsequent visits. - Symptomatic hypertension: Hypertension associated with symptoms ( e.g. , headache, light-headedness, vertigo, tinnitus, episodes of fainting or other symptoms indicative of hypertension) that resolve after the blood pressure is controlled within the normal range. - Asymptomatic hypertension: SBP >140 mmHg and/or DBP >90 mmHg in the absence of the above symptoms.		
(Scenario A) 
 
Asymptomatic and persistent SBP of <math>\geq</math>140 and <160 mmHg, or DBP <math>\geq</math>90 and <100 mmHg, or
 
 Clinically significant increase in DBP of 20 mmHg (but still below 100 mmHg).	
 
Adjust current or initiate new antihypertensive medication(s).
 
Titrate antihypertensive medication(s) during the next 2 weeks to achieve well-controlled BP. If BP is not well-controlled within 2 weeks, consider referral to a specialist and go to scenario (B).
 
	Continue trametinib at the current dose.
(Scenario B) 
 
Asymptomatic SBP <math>\geq</math>160 mmHg, or DBP <math>\geq</math>100 mmHg, or
 
 Failure to achieve well-controlled BP within 2 weeks in Scenario A.	
 
Adjust current or initiate new antihypertensive medication(s).
 
Titrate antihypertensive medication(s) during the next 2 weeks to achieve well-controlled BP.
 
	
 
Interrupt trametinib if clinically indicated.
 
Once BP is well-controlled, restart trametinib reduced by one dose level.a
 

(Scenario C) 
 
Symptomatic hypertension or
 
 Persistent SBP $\geq$ 160 mmHg, or DBP $\geq$ 100 mmHg, despite antihypertensive medication and dose reduction of trametinib	
 
Adjust current or initiate new antihypertensive medication(s).
 
Titrate antihypertensive medication(s) during the next 2 weeks to achieve well-controlled BP.
 
Referral to a specialist for further evaluation and follow-up is recommended.
 
	
 
Interrupt trametinib.
 
Once BP is well-controlled, restart trametinib reduced by one dose level.a
 

(Scenario D) Refractory hypertension unresponsive to above interventions or hypertensive crisis.	Continue follow-up per protocol.	Permanently discontinue trametinib.
a. Escalation of trametinib to previous dose level can be considered if BPs remain well controlled for 4 weeks after restarting of trametinib. Approval from Medical Monitor is required.		

